4.5.4.4.3 Nivolumab Dose Discontinuation

Nivolumab treatment should be permanently discontinued for the following:

- Any Grade 2 drug-related uveitis, eye pain or blurred vision that does not respond to topical therapy and does not improve to Grade 1 severity within the re-treatment period OR requires systemic treatment
- Any Grade 3 non-skin, drug-related AE lasting > 7 days or recurs, with the following exceptions for laboratory abnormalities, drug-related uveitis, pneumonitis, bronchospasm, neurologic toxicity, hypersensitivity reactions, infusion reactions, and endocrinopathies:
 - Grade 3 drug-related uveitis, pneumonitis, bronchospasm, neurologic toxicity, myocarditis, hypersensitivity reaction, or infusion reaction of any duration requires discontinuation
 - Grade 3 drug-related endocrinopathies adequately controlled with only physiologic hormone replacement do not require discontinuation. Adrenal insufficiency requires discontinuation regardless of control with hormone replacement.
 - Grade 3 drug-related laboratory abnormalities do not require treatment discontinuation except:
 - ◆ Grade 3 drug-related thrombocytopenia > 7 days or associated with bleeding requires discontinuation
 - ◆ Grade \geq 3 drug-related AST, ALT or Total Bilirubin requires discontinuation*
 - ◆ Concurrent AST or ALT $>$ 3 x ULN and total bilirubin $>$ 2x ULN

* In most cases of Grade 3 AST or ALT elevation, study treatment will be permanently discontinued. If the investigator determines a possible favorable benefit/risk ratio that warrants continuation of study treatment, a discussion between the investigator and the BMS Medical Monitor/designee must occur.

- Any Grade 4 drug-related adverse event or laboratory abnormality (including but not limited to creatinine, AST, ALT, or Total Bilirubin), except for the following events which do not require discontinuation:
 - Grade 4 neutropenia \leq 7 days
 - Grade 4 lymphopenia or leukopenia or asymptomatic amylase or lipase
 - Isolated Grade 4 electrolyte imbalances/abnormalities that are not associated with clinical sequelae and are corrected with supplementation/appropriate management within 72 hours of their onset
 - Grade 4 drug-related endocrinopathy adverse events, such as, hyper- or hypothyroidism, or glucose intolerance, which resolve or are adequately controlled with physiologic hormone replacement (corticosteroids, thyroid hormones) or glucose-controlling agents, respectively, may not require discontinuation after discussion with and approval from the BMS Medical Monitor.

- Any event that leads to delay in dosing lasting > 8 weeks from the previous dose requires discontinuation, with the following exceptions:
 - *Dosing delays to allow for prolonged steroid tapers to manage drug-related adverse events are allowed. Prior to re-initiating treatment in a subject with a dosing delay lasting > 8 weeks from the previous dose, the BMS medical monitor must be consulted. Tumor assessments should continue as per protocol even if dosing is delayed/interrupted. Periodic study visits to assess safety and laboratory studies should also continue as clinically indicated during such dosing delays/interruption.*
 - *Dosing delays lasting > 8 weeks from the previous dose that occur for non-drug-related reasons may be allowed if approved by the BMS medical monitor. Prior to re-initiating treatment in a subject with a dosing delay lasting > 8 weeks, the BMS medical monitor must be consulted. Tumor assessments should continue as per protocol even if dosing is delayed/interrupted. Periodic study visits to assess safety and laboratory studies should also continue as clinically indicated during such dosing delays/interruption.*
- Any adverse event, laboratory abnormality, or intercurrent illness which, in the judgment of the Investigator, presents a substantial clinical risk to the subject with continued nivolumab dosing.
- At investigator's discretion, based on the safety results from the interim analysis and subject's derived clinical benefit (as of 23-Aug-2018).

Additional criteria for nivolumab dose discontinuation are included in the nivolumab IMAE management algorithm in [Appendix 5](#).

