4.5.4.4.1 Dose Delay/Interruption Criteria for Nivolumab

Nivolumab administration should be delayed for the following:

- Grade 2 non-skin, drug-related AE, with the exception of fatigue
- Grade 2 drug-related creatinine, AST, ALT and/or Total Bilirubin abnormalities
- Grade 3 skin, drug-related AE
- Grade 3 drug-related laboratory abnormality, with the following exceptions:
 - Grade 3 lymphopenia or asymptomatic amylase or lipase does not require dose delay
 - Grade ≥ 3 AST, ALT, Total Bilirubin will require dose discontinuation (see [Section 4.5.4.4.3](#))
- Any adverse event, laboratory abnormality, or intercurrent illness which, in the judgment of the investigator, warrants delaying the dose of study medication.

Participants who require delay of nivolumab should be re-evaluated weekly or more frequently if clinically indicated and resume nivolumab dosing when re-treatment criteria are met.

Additional criteria for nivolumab dose delay/interruption are included in the nivolumab IMAE management algorithm in Appendix 5.

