4.5.4.4.2 Criteria to Resume Treatment with Nivolumab

Subjects may resume treatment with nivolumab when the drug-related AE(s) resolve(s) to Grade ≤ 1 or baseline, with the following exceptions:

- Subjects may resume treatment in the presence of Grade 2 fatigue.
- Subjects who have not experienced a Grade 3 drug-related skin AE may resume treatment in the presence of Grade 2 skin toxicity.
- For participants with Grade 2 AST, ALT and/or Total Bilirubin abnormalities, dosing may resume when laboratory values return to baseline and management with corticosteroids, if needed, is complete.
- Drug-related pulmonary toxicity, diarrhea or colitis must have resolved to baseline before treatment is resumed. Participants with persistent Grade 1 pneumonitis after completion of a steroid taper over at least 1 month may be eligible for retreatment if discussed with and approved by BMS Medical Monitor (or designee).

Participants with drug-related endocrinopathies adequately controlled with only physiologic hormone replacement may resume treatment after consultation with the BMS Medical Monitor (or

designee). Adrenal insufficiency requires discontinuation regardless of control with hormone replacement.

Dose delay/interruption of nivolumab which results in treatment interruption of > 8 weeks require treatment discontinuation, with exceptions as noted in Section 4.5.4.4.3. There will be no dose reductions for nivolumab.

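### The Grade 4 endocrinopathy exception to stopping nivolumab does not exclude adrenal insufficiency, although two other rules require discontinuation for it regardless of hormone control

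*Combined protocol and SAP*

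**What the plan says.** Three places in the nivolumab dosing rules deal with endocrinopathies.

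- **Section 4.5.4.4.2 (resuming nivolumab).** "Participants with drug-related endocrinopathies adequately controlled with only physiologic hormone replacement may resume treatment after consultation with the BMS Medical Monitor". The paragraph then adds, with no grade stated: "Adrenal insufficiency requires discontinuation regardless of control with hormone replacement".
- **Section 4.5.4.4.3, Grade 3 sub-bullet.** "Grade 3 drug-related endocrinopathies adequately controlled with only physiologic hormone replacement do not require discontinuation". The adrenal sentence follows again, word for word.
- **Section 4.5.4.4.3, Grade 4 bullet.** The default is permanent discontinuation, "except for the following events which do not require discontinuation". The endocrinopathy entry in that list covers "Grade 4 drug-related endocrinopathy adverse events, such as, hyper- or hypothyroidism, or glucose intolerance". The exemption then depends on the event being under control. It is worded for events "which resolve or are adequately controlled with physiologic hormone replacement (corticosteroids, thyroid hormones) or glucose-controlling agents, respectively, may not require discontinuation". It closes with the approval condition: such events "may not require discontinuation after discussion with and approval from the BMS Medical Monitor". The adrenal sentence does not appear.

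Sections 4.5.4.4.1 and 4.5.4.4.3 each refer to Appendix 5 for additional criteria, on delay and on discontinuation respectively. Appendix 5 contains an endocrinopathy algorithm, but its chart is not shown in the available text.

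**The concern.** This is a safety stopping rule, and the documents give two answers for the same patient. Someone who applies the Grade 4 entry alone may conclude that nivolumab can continue if the Medical Monitor agrees. Someone who applies 4.5.4.4.2 concludes that it must stop. The less severe Grade 3 event must stop under its own sub-bullet, so the rule becomes more lenient as severity rises.

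The rule is still in use. Under Revised Protocol 03, Section 3.1 lets subjects in the N-Pd and NE-Pd arms stay on treatment at the investigator's judgement. Section 3.5 directs investigators to Section 4.5.4 for further reasons to stop nivolumab permanently, and 4.5.4.4.3 is the list under that heading. The Medical Monitor, who has to approve or refuse, works from the same text.

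**Working it through.** The protocol gives no figure to reproduce here, so the check is a comparison of texts.

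**Step 1: does adrenal insufficiency fall within the Grade 4 entry?** The entry describes a class, drug-related endocrinopathies, and introduces the thyroid and glucose disorders as examples. It then lists corticosteroids among the physiologic replacements. None of the named examples is naturally treated with corticosteroid replacement, so the wording reaches beyond them. Adrenal insufficiency is not named; it comes in by inference from the open list and the corticosteroid reference.

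**Step 2: apply each rule to drug-related adrenal insufficiency controlled on replacement steroids.**

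| Rule | Grade covered | Adrenal sentence present | Result |
|---|---|---|---|
| 4.5.4.4.2, resume rule | None stated | Yes | Discontinue |
| 4.5.4.4.3, Grade 3 sub-bullet | 3 | Yes | Discontinue |
| 4.5.4.4.3, Grade 4 entry | 4 | No | Continuation possible with Medical Monitor approval |

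Two of the three endocrinopathy provisions carry the sentence. The one for the most severe grade does not.

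**Step 3: what kind of conflict is it?** Against 4.5.4.4.2 the inconsistency is direct, because that sentence has no grade limit and so covers Grade 4. Against the Grade 3 sub-bullet, read as applying to Grade 3 only, it is a reversed severity ordering and not a strict contradiction.

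**Step 4: does another rule settle it?** The concomitant-steroid rules do not: Section 3.4.1 allows steroids to treat an adverse event, and Section 3.4.3 permits adrenal replacement doses. Nothing in 4.5.4.4.2 or 4.5.4.4.3 says which of the two takes precedence. The Appendix 5 chart might address the case, but it could not be read.

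**Step 5: what limits the exposure?** The Grade 4 list has four entries: short neutropenia; lymphopenia, leukopenia or asymptomatic amylase or lipase; isolated electrolyte abnormalities; and endocrinopathies. Only the last needs Medical Monitor approval. Section 3.1 reports 75 subjects randomized to N-Pd and 24 to NE-Pd, so 75 + 24 = 99 were assigned to a nivolumab arm; an unstated number also crossed over to NE-Pd. The documents give neither the number still on nivolumab nor the rate of this event.

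**The case against.** The strongest reply is that the texts can be obeyed together. The adrenal sentence is specific and mandatory, carries no grade in its own words, and appears twice, once within 4.5.4.4.3 itself. The Grade 4 entry is general and permissive. Stopping for adrenal insufficiency and seeking approval for other endocrinopathies satisfies every sentence. The named examples are not adrenal, and the treatments are tied to them by the word respectively. A separate bullet in 4.5.4.4.3 also requires stopping whenever the investigator sees a substantial clinical risk.

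Much of this stands. The reconciling reading is reasonable and probably the one intended. But the reader has to supply it. The sponsor did not rely on 4.5.4.4.2 alone at Grade 3, where it repeated the sentence, so its absence at Grade 4 could be taken as deliberate. The corticosteroid reference points the same way.

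Two stronger readings are tempting and are not supported:

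- A reader might infer that the protocol expressly permits nivolumab to continue in Grade 4 adrenal insufficiency. It does not. The condition is never named in that entry, and continuation is neither automatic nor available without approval.
- A reader might infer that the sentence in 4.5.4.4.2 applies only after a hold, and that a Grade 4 case may never reach it because the graded delay triggers in 4.5.4.4.1 stop at Grade 3, leaving only the judgement bullet: "Any adverse event, laboratory abnormality, or intercurrent illness which, in the judgment of the investigator, warrants delaying the dose of study medication". The sentence stands under a resume heading, but it requires discontinuation and sets no condition of a prior hold. Section 4.5.4.4.1 also points to Appendix 5 for further delay criteria, so its own bullets are not the full list.

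**Conclusion.** The inconsistency is real and minor. As written, the Grade 4 entry leaves open an outcome that 4.5.4.4.2 rules out, and it treats the more severe event more leniently than the Grade 3 sub-bullet does. It goes beyond missing detail, because a stated exception and a stated mandatory rule give different answers with no order of precedence.

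Only subjects still on nivolumab who develop hormone-controlled Grade 4 drug-related adrenal insufficiency are affected. That group is likely to be very small, but the documents do not allow a count. There is no effect on an endpoint, sample size, error rate or analysis.

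The conclusion assumes that the list of Grade 4 endocrinopathies is open, as its wording indicates. It is also limited by the unseen Appendix 5 chart. A stricter chart could settle practice, but the body text would still be inconsistent, since it cites the appendix for additional criteria and not as a replacement.

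**What to change.** Append to the Grade 4 endocrinopathy entry in 4.5.4.4.3 the sentence the protocol already uses twice: "Adrenal insufficiency requires discontinuation regardless of control with hormone replacement". Keep the reference to corticosteroids, which may apply to other endocrinopathies in the open list. Check that the Appendix 5 endocrinopathy chart agrees, for both delay and discontinuation, and align it if it does not. If the sponsor does intend discretion at Grade 4, it should say so and amend 4.5.4.4.2 to match.

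The cost is one ten-word sentence, a check of one chart, and a notice to sites and Medical Monitors. No assessment is added.

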4.5.5 Recommended Dose Reduction

The criteria presented in this section for dose modification of dexamethasone and pomalidomide are meant as general guidelines. They are based on current US standards of clinical practice. Local standards may differ and may be followed. Dose modification may occur in the setting of lower grade toxicity if the investigator, in consultation with the Medical Monitor/Sponsor, believes that it is in the interest of subject safety.

4.5.5.1 Nivolumab and Elotuzumab

No dose reductions are allowed for nivolumab or elotuzumab.

4.5.5.2 Dexamethasone

Dexamethasone dose reductions for toxicity must be performed as clinically indicated. Recommended management is described in [Table 4.5.5.2-1](#) and [Table 4.5.5.2-2](#). Deviations to the recommended dose reductions are allowed based on the clinical judgment of the investigator.

Table 4.5.5.2-1: Dexamethasone Dose Reductions

CTCAE Category	Adverse Event	Treatment Adjustment
Gastrointestinal	Dyspepsia, gastric or duodenal ulcer, gastritis Grade 1 - 2 (requiring medical management)	Treat with a proton pump inhibitor. If symptoms persist despite above measures, decrease by 1 dose level.
	≥ Grade 3 (requiring hospitalization or surgery)	Hold dexamethasone until symptoms are adequately controlled. Reduce by 1 dose level and resume along with concurrent therapy with a proton pump inhibitor. If symptoms persist despite above measures, reduce to dose level -3 (dose withheld).
	Acute pancreatitis	Reduce to dose level -3 (dose withheld).
Cardiovascular	Edema ≥ Grade 3 (limiting function and unresponsive to therapy or anasarca)	Use diuretics as needed, and decrease dexamethasone by 1 dose level. If edema persists despite above measures, decrease by another dose level.
Neurology	Confusion or Mood alteration ≥ Grade 2 (interfering with function ± interfering with activities of daily living)	Hold dexamethasone until symptoms resolve. Decrease by 1 dose level and resume. If symptoms persist despite above measures, decrease by another dose level.
Musculoskeletal	Muscle weakness ≥ Grade 2 (symptomatic and interfering with function ± interfering with activities of daily living)	Hold dose until muscle weakness is ≤ Grade 1. Decrease dexamethasone by 1 dose level and resume. If weakness persists despite above measures, decrease by another dose level.
Metabolic	Hyperglycemia ≥ Grade 3 or higher	Treat with insulin or oral hypoglycemics as needed. If uncontrolled despite above measures, decrease by 1 dose level until glucose levels are satisfactory.
Constitutional	Insomnia ≥ Grade 2	Decrease by 1 dose level and resume.

Dose reduction for persistent Grade 2 or Grade ≥ 3 AEs believed to be related to dexamethasone and not listed above are permitted. Dose reductions should follow the guidance in Table 4.5.5.2-1 and [Table 4.5.5.2-2](#).

For subjects receiving elotuzumab, regardless of dexamethasone dose reduction, at least 8 mg of the weekly dexamethasone dose must be administered IV as part of the premedication for elotuzumab with the remainder of the weekly dexamethasone dose administered orally as described in [Section 4.5.1.3.2](#). Contact the Medical Monitor to discuss dexamethasone IV premedication for subjects in the investigational arm who reach dose level -3 and must discontinue dexamethasone due to dose limiting toxicity.

On days without elotuzumab, no IV dexamethasone should be administered.

Table 4.5.5.2-2: Dexamethasone Dose Levels

Dose Level	Reducing Dexamethasone on Weeks with Elotuzumab		Reducing Dexamethasone on Weeks Without Elotuzumab	
	PO	IV	PO	IV
0	≤ 75 years old - 28 mg	8 mg	≤ 75 years old - 40 mg	N/A
	> 75 years old - 8 mg		> 75 years old - 20 mg	
-1	≤ 75 years old - 12 mg	8 mg	≤ 75 years old - 20 mg	N/A
	> 75 years old - 2 mg		> 75 years old - 12 mg	
-2	≤ 75 years old - 0 mg	8 mg	≤ 75 years old - 12 mg	N/A
	> 75 years old - 0 mg		> 75 years old - 8 mg	
-3	≤ 75 years old - 0 mg	Contact Medical Monitor	≤ 75 years old - 0 mg	N/A
	> 75 years old - 0 mg		> 75 years old - 0 mg	

4.5.5.3 Pomalidomide

Below are the recommended dose adjustments for the management of thrombocytopenia and neutropenia judged by the investigator to be related to pomalidomide. Information in Table 4.5.5.3-1 and Table 4.5.5.3-2 is based on pomalidomide prescribing information, which contains additional guidance on pomalidomide dosing ^{28,29}. Investigators should follow the guidelines in the prescribing information for pomalidomide. Some clinically relevant events and their management are presented below.

Table 4.5.5.3-1: Treating Thrombocytopenia Related to Pomalidomide

When Platelet Count:	Recommended Course:
• Fall to < 25,000 per mm ³	• Interrupt pomalidomide treatment, follow Complete Blood Count weekly.
• Return to > 50,000 per mm ³	• Resume pomalidomide at 3 mg daily
• For each subsequent drop < 25,000 mm ³	• Interrupt pomalidomide treatment
• Return to ≥ 50,000 mm ³	• Resume pomalidomide at 1 mg less than previous dose

Table 4.5.5.3-2: Treating Neutropenia Related to Pomalidomide

When Neutrophil Count:	Recommended Course:
• Fall to < 500 per mm ³ or febrile neutropenia (fever ≥ 38.5°C and ANC < 1,000 mm ³)	• Interrupt pomalidomide treatment, follow Complete Blood Count weekly.
• ANC returns to ≥ 1000 per mm ³	• Resume pomalidomide at 3 mg daily
• For each subsequent drop < 500 mm ³	• Interrupt pomalidomide treatment
• Return to ≥ 1000 mm ³	• Resume pomalidomide at 1 mg less than previous dose

ANC, absolute neutrophil count. In case of neutropenia, consider the use of growth factors in subject management.

If necessary to co-administer strong inhibitors of CYP1A2 in the presence of strong inhibitors of CYP3A4 and P-glycoprotein, consider reducing pomalidomide dose by 50%.^{28,29}

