4.5.1.1.1 Pomalidomide

Administered orally at the dose of 4 mg daily on Days 1 - 21 of each 28 day cycle. Pomalidomide should be taken in accordance with local label.

Subjects should be instructed that if a dose of pomalidomide has been missed and it has been less than 12 hours since the subject's regular dosing time, to take pomalidomide as soon as the subject remembers. If it has been more than 12 hours, the dose must be skipped. Subjects should not take 2 doses at the same time.

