Elotuzumab Infusion		X								Section 4.5.1 for Elotuzumab window, Nivolumab is infused before Elotuzumab in the NE-Pd arm/Elotuzumab premedications can be administered before nivolumab.
Nivolumab Infusion		X								Section 4.5.1 Nivolumab is infused first on the NE-Pd arm
Pomalidomide Administration		Day 1 - 21 of Cycle								Dispense pomalidomide on Day 1 of each cycle per the local risk management program or the Pomalidomide Pregnancy Risk Prevention Plan (Appendix 6).
Dexamethasone Administration		X	X	X	X					Dexamethasone dosing per Section 4.5.1

Table 5.1-4: Procedural Outline (CA209602) Cycles 5 and Beyond

Procedure	Local Lab (LL) or Central Lab (CL)	Day 1	Day 8	Day 15	Day 22	Rest Days 23-28	End Of Treatment	Follow up visits: Days 30 & 100 post end of treatment (+/- 7 day window)	Survival Follow-Up (+/-14 day window)	Notes

Table 5.1-4: Procedural Outline (CA209602) Cycles 5 and Beyond

Procedure	Local Lab (LL) or Central Lab (CL)	Day 1	Day 8	Day 15	Day 22	Rest Days 23-28	End Of Treatment	Follow up visits: Days 30 & 100 post end of treatment (+/- 7 day window)	Survival Follow-Up (+/-14 day window)	Notes

5.1.1 *Retesting During Screening or Lead-in Period*

Retesting of laboratory parameters and/or other assessments within any single screening will be permitted (in addition to any parameters that require a confirmatory value).

Any new result will override the previous result (ie, the most current result prior to Randomization) and is the value by which study inclusion will be assessed, as it represents the subject's most current, clinical state.

Laboratory parameters and/or assessments that are included in [Table 5.1-1](#), Screening Procedural Outline may be repeated in an effort to find all possible well-qualified subjects. Consultation with the Medical Monitor may be needed to identify whether repeat testing of any particular parameter is clinically relevant.

5.2 *Study Materials*

The following will be distributed to sites for use in this study:

- NCI CTCAE booklets version 4.0
- Elotuzumab Investigator Brochure
- Nivolumab Investigator Brochure
- Pomalidomide (Pomalyst®) Package Insert
- Site Manual for operation of IWRS
- Subject Dosing Diary
- Subject Quality of Life Questionnaires
- Serious Adverse Event (SAE) Case Report Form (CRF) pages
- Pregnancy Surveillance Forms
- Pharmacy Binder
- Laboratory manuals for collection and handling of blood samples
- Laboratory manual for local lab data entry

5.3 *Safety Assessments*

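### As printed, the first-event rows of both pomalidomide cytopenia tables restart at a fixed 3 mg, so a subject already reduced under the other table gets no reduction or a higher dose

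*Combined protocol and SAP*

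**What the plan says.** Every arm starts pomalidomide at the same dose. For the N-Pd arm, Section 4.5.1.1.1 reads "Administered orally at the dose of 4 mg daily on Days 1 - 21 of each 28 day cycle"; Sections 4.5.1.2.1 and 4.5.1.3.1 give the same dose for the other two arms.

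Tables 4.5.5.3-1 (thrombocytopenia) and 4.5.5.3-2 (neutropenia) have the same structure. At the first qualifying fall the drug is interrupted. On recovery the advice is "Resume pomalidomide at 3 mg daily". For each further fall of that same count the advice on recovery is "Resume pomalidomide at 1 mg less than previous dose". Neither table refers to the other, and the first-event row sets no condition on the dose being taken.

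Three statements limit the force of the tables:

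- Section 4.5.5 says that its criteria "for dose modification of dexamethasone and pomalidomide are meant as general guidelines", and it allows local standards to be used.
- Section 4.5.5.3 says that the content of the tables "is based on pomalidomide prescribing information, which contains additional guidance on pomalidomide dosing", and adds: "Investigators should follow the guidelines in the prescribing information for pomalidomide".
- The study materials in Section 5.2 include the "Pomalidomide (Pomalyst®) Package Insert".

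**The concern.** The first-event row is an absolute dose and the later-event row is a relative step. They agree only when the first event in a table occurs at 4 mg. Because each table counts its own events, a subject can have a first event in one table after one or more reductions under the other. The printed line then keeps or raises the dose after a severe cytopenia judged related to pomalidomide, although the next row of the same table steps down. The neighbouring dexamethasone guidance (Section 4.5.5.2) works by dose levels relative to the current one and cannot produce this result.

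What is at stake is dosing safety for subjects who continue treatment.

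**Working it through.** **Inputs.** Starting dose 4 mg (Section 4.5.1.1.1). First event in a table: restart at 3 mg. Later event in the same table: previous dose minus 1 mg (both from Section 4.5.5.3). Capsule strengths 1, 2, 3 and 4 mg (Table 4.1), so 1 mg is the lowest listed.

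**The plan's own figure.** From 4 mg, a first event gives 3 mg: 3/4 - 1 = -25%. The printed rule works as a one-step reduction here.

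**Other doses at the first event of a type.** With d the dose at the event, the printed restart is 3 and the change is 3/d - 1. The proposed restart is min(3, d - 1).

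| Dose at event | Printed restart | Change | Proposed restart | Change |
|---|---|---|---|---|
| 4 mg | 3 mg | -25% | 3 mg | -25% |
| 3 mg | 3 mg | 0% | 2 mg | 2/3 - 1 = -33% |
| 2 mg | 3 mg | 3/2 - 1 = +50% | 1 mg | 1/2 - 1 = -50% |
| 1 mg | 3 mg | 3/1 - 1 = +200% | formula gives 0 mg | stop, or decide with the Medical Monitor |

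**Can these doses be reached?** Yes, under the tables' own rules from 4 mg. Write N for a neutropenia event and T for a thrombocytopenia event; the results are the same with N and T exchanged.

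| Events | Printed path | Proposed path |
|---|---|---|
| N, T | 4-3-3 | 4-3-2 |
| N, N, T | 4-3-2-3 | 4-3-2-1 |
| N, N, N, T | 4-3-2-1-3 | 4-3-2-1, then stop or decide |

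**Is it plausible to have both cytopenias?** Section 1.3.3 reports grade 3-4 neutropenia in 48% and thrombocytopenia in 22% of subjects on pomalidomide with low-dose dexamethasone in an earlier phase 3 trial. From these two rates alone, the share with both lies anywhere between 0% and 22%; if the two were independent, which is an assumption, it would be 0.48 x 0.22 = about 11%. This is context only. The tables are triggered by specific counts (and febrile neutropenia), not by grade 3-4, and the documents give no joint rate. The first path needs one event of each type. The two paths that raise the dose need more events and should be rarer.

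**How many subjects could be affected?** Section 3.1 gives 75 + 71 + 24 = 170 randomized. Section 1.7 reports deaths of 29% (N-Pd), 27% (Pd, 19 subjects including crossovers) and 50% (NE-Pd). On the randomized numbers that is about 22 + 19 + 12 = 53, leaving about 170 - 53 = 117 alive at that cutoff. Discontinuations lower this further. An affected subject must also be below 4 mg already and then have a first event of the other type. The documents give no count for either condition.

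**The case against.** The strongest reply is that the tables are an extract of a document that governs. Investigators are told to follow the prescribing information, the insert is supplied to sites, local standards may be used, and Section 4.5.4 sends questions about dose interruption to the Medical Monitor. If the label covers a subject who is already reduced, the gap is closed by reference. If it has the same wording, the change would depart from it. The section is titled Recommended Dose Reduction, and the fixed 3 mg plainly presumes a subject on 4 mg, so few physicians would use it to raise a dose.

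Much of this stands. It lowers the practical weight, and it is why the label check comes first. It does not make the printed line right. These are the only restart doses that the protocol prints, nothing else in it caps the restart at the current dose, and the discretion in Section 4.5.4.3 concerns interruption, not the restart dose. It is also fair that the documents do not prove 2 mg to be the required dose after a first event of the other type at 3 mg. The argument for 2 mg is consistency with the step-down in the next row.

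A reader might also infer a second route to a raised dose. For certain strong inhibitors given together, Section 4.5.5.3 says to "consider reducing pomalidomide dose by 50" percent, so a subject at 2 mg for that reason would go 4-2-3 after one cytopenia. This is only a possible literal reading. The reduction is optional and separate, Section 3.4.1 says to avoid such co-administration unless medically necessary, and nothing says that a cytopenia restart cancels it.

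**Conclusion.** The point holds for the printed text of both tables: the first-event restart is correct at 4 mg, gives no reduction at 3 mg, and raises the dose by 50% at 2 mg and by 200% at 1 mg. This rests on counting events within each table, as the rows are worded, and on no other protocol text conditioning the 3 mg line.

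It is a minor safety correction. The tables are not binding, they defer to a label that is not in the documents, enrollment is closed, and only subjects still on treatment can be affected. Section 3.1 lets N-Pd and NE-Pd subjects continue.

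Some stronger conclusions are tempting and not supported. The documents do not show that an increase was intended; the line reads as a drafting gap. They do not show that any subject was dosed this way. The 170 randomized are not an estimate of those affected, and are a loose ceiling for those still on treatment. Nothing here changes the primary endpoint or its planned analysis.

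**What to change.** First have the sponsor's clinical team check the current prescribing information. Then change the first-event restart line in both tables to: *3 mg daily, or 1 mg less than the dose at the time of the event, whichever is lower; never above the dose at the time of the event*. Nothing changes for a subject at 4 mg.

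The formula gives 0 mg for an event at 1 mg, so the fix must also cover that case: discontinue pomalidomide, or decide with the Medical Monitor. A useful optional addition is the restart dose after a repeat febrile neutropenia, because the later-event row of the neutropenia table names only the count.

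The cost is the label check, one changed line and one added instruction in each table, and communication to sites. Section 9.1.1 requires IRB/IEC approval of an amendment before use, except for an immediate hazard, or notification of the IRB/IEC if the change is made by administrative letter. No new data or procedures are needed.
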